 272 effectiveness analysis to identify the best approach to initial airway management during OHCA.

273 Randomisation by patient is impractical; we will therefore randomise by paramedic.

274

275 Paramedics will be recruited from four NHS ambulance services with favourable characteristics.

276

277 The NHS ambulance services are:

278

- 279 • South Western Ambulance Service NHS Foundation Trust (SWAST)
- 280 • East of England Ambulance Service NHS Trust
- 281 • East Midlands Ambulance Service NHS Trust
- 282 • Yorkshire Ambulance Service NHS Trust

283

284 The College of Paramedics is also fully supportive of the study.
285 Hospitals receiving OHCA patients from these ambulance services will also be taking part.

286

287 **4.3 Key design features to minimise bias**

288

289 **4.3.1 Selection bias/allocation bias (systematic differences between baseline characteristics of the groups that** 290 **are compared)**

291

292 This type of bias is usually ruled out by concealed randomisation in a trial that randomises individual patients. This is
293 not necessarily the situation with a cluster-randomised trial because inclusion of only a small number of clusters can
294 cause chance imbalances (not bias *per se*) between the groups. Since AIRWAYS-2 will recruit about 1300 paramedics
295 chance imbalances will not be a problem.
296

297 Even with concealed allocation of clusters (paramedics), bias can arise from recruitment of a different proportion of
298 eligible individuals among paramedics allocated to different airway management strategies. Moreover, even if these
299 proportions do not differ overall, differential recruitment of eligible individuals among paramedics may happen, with
300 paramedics assigned to different airway management strategies recruiting different kinds of patients (but the same
301 overall proportion). In this trial, we will avoid this bias by using a combination of methods to identify all eligible
302 patients, including direct notifications by ambulance clinicians and review of routine ambulance service data to ensure
303 >99% of the eligible patients are included (see section 5.6.1)

304

305 Bias could also be introduced by applying inclusion criteria in a biased manner, i.e. including >99% of eligible patients
306 will not be sufficient if paramedics in different groups consider different patients to be eligible. The most obvious

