354 • Qualified to practice tracheal intubation in their current clinical role
355

356 **Paramedic Exclusion criteria**

357

- 358 • Paramedics working in non-clinical and managerial roles not routinely* attending OHCA
359

360 *Routinely is defined as usually attending at least 2 OHCA patients where resuscitation is attempted each year. This
361 however will not be a 'hard' exclusion criterion.
362

363 **4.4.2 Inclusion and exclusion criteria for patients:**

364

365 **Patient Inclusion Criteria**

366

- 367 • Patient known or believed to be 18 years of age or older
368 • Patient has had a non-traumatic cardiac arrest outside hospital
369 • Patient must be attended by a paramedic who is participating in the trial and is either the 1st or 2nd paramedic
370 to arrive at the patient's side.*1
371 • Resuscitation is commenced or continued by ambulance staff or responder*2
372

373 *1. The participating paramedic will manage the patient's airway, according to their allocation. If both the 1st and 2nd
374 paramedic are participating in the trial, the patient's airway will be managed according to the allocation of the 1st
375 paramedic to arrive at the patient's side (usually designated as the "attendant" within the ambulance service).
376

377 If the 1st paramedic to arrive is not an AIRWAYS-2 paramedic, but the 2nd paramedic is, the patient will be enrolled
378 in the study unless an advanced airway intervention has already occurred (advanced airway intervention is defined as
379 either a SAD or tracheal tube being present in the patient's mouth) at the point that the second paramedic arrives at the
380 patient's side.

381

382 If a 3rd or subsequent paramedic arrives at the patient's side, and the first two paramedics are not participating in the
383 trial but the 3rd or subsequent paramedic is participating, the patient will be excluded (such an exclusion may need to
384 be determined retrospectively).

385

386 *2 Circumstances in which resuscitation should and should not be attempted are described in national guidelines. The
387 Joint Royal Colleges Ambulance Liaison Committee (JRCALC) Recognition of Life Extinct (ROLE) criteria are
388 currently used by all ambulance trusts to determine when a resuscitation attempt is inappropriate, and these criteria will
389 be applied in this trial. These criteria are objectively defined, but the frequency of attempted resuscitation in both

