390 groups will be regularly examined by the DMSC to identify any bias in the commencement of resuscitation attempts.

391

392 **Patient Exclusion criteria**

393

- 394 • Patient detained by Her Majesty's Prison Service
- 395 • Previously recruited to the trial (determined retrospectively)
- 396 • Resuscitation considered inappropriate (see below)
- 397 • Advanced airway management inserted by another HCPC registered paramedic, doctor or nurse already in
398 place when AIRWAYS-2 paramedic arrives at patient's side (when the first paramedic to arrive is not
399 participating in AIRWAYS-2)
- 400 • Known to already be enrolled in another pre-hospital randomised trial
- 401 • Mouth opening <2 cm

402

403 This last exclusion has been applied because SADs are not designed for use in patients with significantly reduced
404 mouth opening. There is a risk of post-randomisation bias being introduced by this exclusion criteria, but in our
405 feasibility study only 2/711 patients (0.3%) were excluded on these grounds. We will monitor this exclusion, under the
406 guidance of the DMSC, and should the exclusion rate exceed 1% we will take action to address this through enhanced
407 training and supervision.

408

409 Standardised guidelines, based on those produced by JRCALC, will be applied to determine patients for whom a
410 resuscitation attempt is inappropriate. This is the case when there is no chance of survival, the resuscitation attempt
411 would be futile and distressing for relatives, friends and healthcare personnel and where time and resources would be
412 wasted undertaking such measures. When any one or more of the following conditions exist, resuscitation and
413 enrolment in the trial will not take place.

414

- 415 1. massive cranial and cerebral destruction
- 416 2. hemicorporectomy
- 417 3. massive truncal injury incompatible with life (including decapitation)
- 418 4. decomposition/putrefaction
- 419 5. incineration
- 420 6. hypostasis
- 421 7. rigor mortis
- 422 8. A valid do not attempt resuscitation order or an Advanced Directive (Living Will) that states the wish of the
423 patient not to undergo attempted resuscitation
- 424 9. When the patient's death is expected due to terminal illness
- 425 10. Efforts would be futile, as defined by the combination of **all three** of the following being present
- 426 (a) More than 15 minutes since the onset of collapse
- 427 (b) no bystander CPR prior to arrival of the ambulance

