589 computer based system with secure allocation concealment that cannot be changed once allocated, and will allocate the
590 paramedics in a 1:1 ratio to the two groups.

591

592 Randomisation will be carried out by a member of the CTEU Bristol, or appropriately trained member of the research
593 team.

594

595 Code breaking will not be necessary since paramedics will be aware of their allocation, and whilst the intervention is in
596 progress the allocated treatment will be apparent. Furthermore, once the intervention has been completed subsequent
597 in-hospital treatment is not influenced by study allocation.

598

599 **5.2 Procedures to minimise bias**

600

601 **5.2.1 Selection/allocation bias**

602

603 First, established objectively defined criteria will be used by participating paramedics to determine whether a
604 resuscitation attempt is appropriate, and hence whether the patient is eligible (see standardised resuscitation guidelines,
605 section 4.4.2).

606

607 Second, we will institute a programme of regular monitoring by analysing the proportion of cardiac arrests recruited, to
608 detect any imbalances that may be caused by different thresholds for resuscitation. We will also monitor the presenting
609 rhythm, proportion of witnessed and un-witnessed arrests, presence of bystander CPR and time from 999 call to crew
610 arrival.

611

612 If we suspect that a different threshold for resuscitation is being applied by one or more paramedics participating in the
613 trial, the first step will be to identify the personnel involved and ensure that their training in the trial procedures is up to
614 date, and reinforce the essential messages about the rationale for the trial. The trial team will include a local research
615 paramedic in each of the 4 ambulance regions, this person will develop a close working relationships with the
616 participating paramedics, and will be ideally placed to undertake this role.

617

618 **5.2.2 Blinding**

619

620 Because of the nature of the intervention, ambulance clinicians cannot be blinded, and will be aware of treatment
621 allocations, with an attendant risk of performance bias. However control room personnel will be blinded to the
622 allocation of paramedics, and follow established protocols when allocating resources to a possible cardiac arrest. This
623 will ensure that there is no bias in despatch.

624

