1940 the best fit in terms of information criteria such as AIC, BIC and likelihood ratio tests will be used.

1941 **6.2.3 Statistical significance**

- 1942 For hypothesis tests two-tailed p-values < 0.05 are considered statistically significant.
- 1943 **6.2.4 Model assumptions**
- 1944 For all methods outlined underlying assumptions will be checked using standard methods, e.g. residual plots,
1945 tests for proportional hazards, etc. If assumptions are not valid then alternative methods of analysis will be
1946 sought. If outlying observations are found which mean models do not fit the data adequately, such
1947 observations will be excluded from the main analyses and comments made in footnotes.
- 1948 **6.2.5 Subgroup analyses**
- 1949 Two subgroup analyses for the primary outcome are specified in the protocol: Utstein comparator group vs
1950 non-comparator group and arrest witnessed by ambulance staff or not (**Figure F7**).
- 1951
- 1952 Due to concerns regarding ventilation success raised during the trial, a subgroup analysis of the primary
1953 outcome comparing patients whose i-gel or intubation airway management attempt(s) were or were not
1954 ‘successful’ during the first and/or second attempt (see section 5.2 for definition) will also be performed. This
1955 analysis will be performed per-protocol and as such will only include patients who received at least one
1956 advanced airway management attempt using an i-gel and/or intubation tube.
- 1957
- 1958 Subgroup effects will be fitted by adding a “sub-group x intervention” interaction term to the analysis model.
- 1959 **6.2.6 Sensitivity analyses**
- 1960 For the primary outcome, the following sensitivity analyses will be performed:
- 1961
 - ITT analysis including only patients who received at least one advanced airway management attempt
1962 using an i-gel and/or intubation tube.
 - Per-protocol analysis including only patients who received at least one advanced airway management
1963 attempt using an i-gel and/or intubation tube (see section 6.2.5 for additional sub-group analysis for
1964 this outcome).
 - ITT analysis including all patients who were attended by an AIRWAYS-2 paramedic but not
1965 resuscitated.
- 1966
- 1967
- 1968 **6.2.7 Missing data**
- 1969 In all tables missing data will be indicated by footnotes. If the amount of missing data differs substantially
1970 between treatment groups potential reasons will be explored.
- 1971 Missing predictors:

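### The exclusion for inappropriate resuscitation has no time point, and Protocol 6.1 and the SAP disagree on whether a patient resuscitated and then excluded is analysed

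*Protocol*

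**What the plan says.** **Who gets in.** The inclusion criterion in Protocol 4.4.2 is "Resuscitation is commenced or continued by ambulance staff or responder". Footnote *1 to that list allows a non-trial paramedic to arrive first and an AIRWAYS-2 paramedic second.

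**Who is taken out.** The exclusion list in the same section has "Resuscitation considered inappropriate (see below". Eleven conditions follow, and if any one is present, resuscitation and "enrolment in the trial will not take place". The text reads as if nothing has yet started. No time point is given.

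**Who judges.** Section 5.2.1 says: "First, established objectively defined criteria will be used by participating paramedics to determine whether a" resuscitation attempt is warranted, and eligibility follows from that. Section 5.2.2 adds: "Because of the nature of the intervention, ambulance clinicians cannot be blinded".

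**What the protocol fears.** Section 4.3.1 accepts that near-complete capture of eligible patients "will not be sufficient if paramedics in different groups consider different patients to be eligible". It names a differential resuscitation threshold as the most obvious source of this bias and promises to prevent, detect and, if necessary, correct it.

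**What is watched.** In footnote *2 to 4.4.2, the frequency of attempted resuscitation in both "groups will be regularly examined by the DMSC to identify any bias in the commencement of resuscitation attempts". Section 5.2.1 also monitors the proportion of arrests recruited, and log (d) in section 5.6 records reasons for ineligibility among resuscitated patients.

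**What is analysed.** Protocol 6.1 keeps enrolled patients later found ineligible, with three exceptions: previous enrolment, a paramedic arriving later than second, and age under 16. The SAP, printed in the same file after the protocol's reference list, restricts the primary population to patients who were resuscitated, attended and eligible (3.7, Population 1a). It takes consciously enrolled but ineligible patients out of the study population (3.5). Its third sensitivity analysis (6.2.6) is an "ITT analysis including all patients who were attended by an AIRWAYS-2 paramedic but not" resuscitated.

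**The concern.** The exclusion operates after paramedics have been allocated, and it is applied by people who know the allocation. Some of its conditions can come to light once resuscitation is under way: a valid do-not-attempt order, an expected death from terminal illness, or the asystole element of the futility rule. Other exclusions in 4.4.2 do carry a timing: previous recruitment is settled retrospectively, and a relative's objection counts at the start of the attempt.

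The protocol describes these patients as having no chance of survival, so nearly all would score mRS 6. If one arm's paramedics exclude more of them, only that arm's denominator shrinks and its good-recovery percentage rises with no device effect. Whether this can happen depends on whether the patients stay in the analysis, and on that the documents disagree.

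**Working it through.** **1. The plan's own figure.** Inputs from Protocol 4.7: 8% v 10%, 5% level (taken as two-sided), 90% power, ICC 0.005, 7 patients per paramedic.

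- n = [1.960·√(2·0.09·0.91) + 1.282·√(0.08·0.92 + 0.10·0.90)]² / 0.02² = 4,301 per group, or 4,401 with continuity correction. Stated: 4,400.
- Design effect = 1 + (7 − 1)·0.005 = 1.03, and 4,401·1.03 gives 4,534. Stated: 4,535.

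The plan's figure reproduces, so 4,535 per arm and 1.03 are used below.

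**2. Following one patient.** A responder or first crew starts resuscitation, an AIRWAYS-2 paramedic is second at the side, and a listed condition is then recognised.

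| Rule | Result for this patient |
|---|---|
| Protocol 4.4.2, inclusion | Met: resuscitation was commenced |
| Protocol 4.4.2, exclusion | Met: no time point limits it |
| Protocol 6.1 | Kept, if already counted as enrolled; not clearly covered if excluded before that |
| SAP 3.5 | Removed, even if consciously enrolled |
| SAP 3.7, Population 1a | Out: not eligible |
| SAP 6.2.6, first and second sensitivity analyses | Out: these narrow the trial population |
| SAP 6.2.6, third sensitivity analysis | Not added: the patient was resuscitated |
| SAP Table T1 | In the excluded column for resuscitated, attended patients, which is not split by arm |

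**3. What an imbalance would do.** Assumptions: no true effect, 9% good recovery in both arms, one arm loses an extra fraction f of its patients, and all of those have a poor outcome. The documents give no value for f.

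- Rate in the affected arm: p_f = 9% / (1 − f)
- SE² = 1.03·[0.09·0.91/4,535 + p_f(1 − p_f)/(4,535(1 − f))]
- z = (p_f − 0.09)/SE
- Two-sided rejection = 1 − Φ(1.96 − z) + Φ(−1.96 − z)

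| f | Patients lost | p_f | Spurious difference (points) | Rejection rate |
|---|---|---|---|---|
| 0 | 0 | 9.00% | 0 | 5.0% |
| 1% | 45 | 9.09% | 0.09 | 5.3% |
| 2% | 91 | 9.18% | 0.18 | 6.0% |
| 3% | 136 | 9.28% | 0.28 | 7.4% |
| 5% | 227 | 9.47% | 0.47 | 11.8% |
| 10% | 454 | 10.00% | 1.00 | 34.3% |

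At f = 5%, SE is 0.625 points and z = 0.474/0.625 = 0.76. At f = 10%, SE is 0.643 points and z = 1.00/0.643 = 1.56. Leaving out the design effect gives about 12% and 35%.

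**The case against.** **The two rules do not contradict each other.** A reader might infer that they do. Meeting an inclusion and an exclusion criterion together is how any exclusion works, and the exclusion normally prevails. That stands: the defect is the missing time point and the disagreement over analysis.

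**Protocol 6.1 already keeps such patients.** A reader might infer that the documents simply drop them. They do not: 6.1 retains anyone already enrolled, and its three exceptions omit this reason. But SAP 3.5 says the opposite. In addition, 6.1 cannot clearly protect a patient for whom enrolment is said not to take place.

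**There is more monitoring than the DMSC check.** A reader might infer that no safeguard sees this group. The count of attempted resuscitations would miss it, since these patients count as attempted. The proportion recruited and the 5.6(d) log could show it. For illustration, assume 30% or 80% of attended arrests are recruited and ignore clustering. A 5% relative shortfall in one arm is then 30% v 28.5% (about 15,117 arrests per arm, z = 1.5/0.52 = 2.9) or 80% v 76% (about 5,669 per arm, z = 4.0/0.78 = 5.1). So the larger imbalances would probably be noticed. The response described in 5.2.1, however, is retraining. Section 4.3.1 promises correction and points to 4.4.2 and to a section 5.3.7 that does not exist (5.3 ends at 5.3.5). Neither the monitoring nor the log changes the analysis.

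**The criteria are listed and largely factual.** Most are gross physical signs. The futility rule requires that there was no bystander CPR before the ambulance arrived, so bystander CPR defeats it. Late discovery is mainly a matter of do-not-attempt orders and expected deaths. This narrows the group but does not empty it.

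**The flow figures may report exclusions by arm.** SAP Figures F1 and F2 are not shown, so this cannot be ruled out. Table T1 alone does not settle what will be reported.

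**Conclusion.** The concern holds in a limited form. The exclusion has no time point and is applied by unblinded, allocated staff. Protocol 6.1 and SAP 3.5/3.7 give opposite answers for an enrolled patient later found ineligible on this ground, and a patient excluded before being counted as enrolled is not clearly covered by 6.1. On the SAP's definitions the group is in no primary-outcome analysis.

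The documents do not show that bias will occur or that it would be large. A between-arm excess of 1–3% leaves the false-positive rate at about 5–7%. About 5% is needed before the distortion (0.47 points) reaches roughly a quarter of the 2-point target, and 10% gives half of it. These figures rest on 9% good recovery, no survivors among those excluded, and an imbalance rate that the documents do not supply. The case for acting is that the protocol itself names this bias and promises to correct it, and the remedy is cheap.

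**What to change.** 1. **Reconcile Protocol 6.1 with SAP 3.5 and 3.7.** For analysis membership only, keep patients who had resuscitation commenced or continued and an AIRWAYS-2 paramedic first or second at the side, as 6.1 states for enrolled patients. Say explicitly that a later finding under this exclusion does not remove them.
2. **Widen the third sensitivity analysis in SAP 6.2.6.** Add patients attended by an AIRWAYS-2 paramedic who were not resuscitated or who were excluded because resuscitation was judged inappropriate.
3. **Report these exclusions by allocated arm and reason**, using the log in section 5.6(d).

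The cost is wording, since the reasons are already logged. The downside is a slightly lower event rate: if 5% more patients were added and all died, 9.0% would become 9.0/1.05 = 8.6%. The design contrast of 8% v 10% would become 7.6% v 9.5%, a difference of 1.9 points.

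All of this concerns who is counted. It says nothing about when resuscitation should start or stop.

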234 with reduced length of stay, enhanced quality of life and reduced use of health and social care resources. We anticipate
235 potential gains for individual patients, the wider NHS and society as a whole.

236

237 This study is likely to lead to rapid and important changes in the treatment protocols recommended by the International
238 Liaison Committee on Resuscitation (ILCOR). This organisation was formed in 1992 to provide an opportunity for the
239 major groups engaged in resuscitation worldwide to work together on CPR and emergency cardiovascular care
240 protocols. ILCOR is composed of the American Heart Association (AHA), the European Resuscitation Council (ERC),
241 the Heart and Stroke Foundation of Canada (HSFC), the Australian and New Zealand Committee on Resuscitation, the
242 Resuscitation Council of Southern Africa (RCSA), the Resuscitation Council of Asia (RCA) and the Inter American

243 Heart Foundation (IAHF). As a result it has truly international reach, and its guidelines are almost universally accepted
244 as being the most up to date and effective in the field.

245

246 **3. AIMS AND OBJECTIVES**

247

248 **Aim:**

249 To determine whether the i-gel, a second-generation SAD, is superior to tracheal intubation in non-traumatic OHCA in
250 adults, in terms of both clinical and cost effectiveness.

251

252 **Objectives:**

253 1. To estimate the difference in the primary outcome of modified Rankin Scale (mRS) at hospital discharge (or 30 days
254 post OHCA) between groups of patients managed by paramedics randomised to use either the i-gel or intubation as
255 their initial airway management strategy following OHCA.

256 2. To estimate differences in secondary outcome measures relating to airway management, hospital stay and recovery
257 at 3 and 6 months (see section 4.6.2) between groups of patients managed by paramedics randomised to use either the
258 i-gel or intubation.

259 3. To estimate the comparative cost effectiveness of the i-gel and intubation, including estimating major in hospital
260 resources and subsequent costs (length of stay, days of intensive and high dependency care, etc.) in each group.

261 **4. PLAN OF INVESTIGATION**

[figure not shown]
262

263 **4.1 Trial schema**

264

265 **Figure 1: Trial schema**

266

267

268

269 **4.2 Trial design**

270

271 This is a parallel two-group multi-centre cluster randomised controlled trial (RCT) and accompanying cost-

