948 For the economic evaluation we will follow established guidelines as set out by the National Institute for Health and
949 Care Excellence (NICE)[48]. The evaluation will be undertaken from an NHS and personal social services perspective.
950 A cost-utility analysis will be conducted, since the primary outcome measure for the economic evaluation will be
951 quality adjusted life years (QALYs) [49], estimated using the EuroQol EQ-5D-5L [50, 51]. These data will be
952 collected for all survivors at hospital discharge and 3 and 6 months after their OHCA. The EuroQol EQ-5D-5L will be
953 administered in person by a research nurse blinded to treatment allocation at discharge. The 3 and 6 month EQ-5D will
954 be co-ordinated by Bristol CTEU and will be administered to the patient/consultee either by telephone, or by a postal
955 or web-based questionnaire. If this proves impractical a research nurse can administer the questionnaire to the
956 patient/consultee at either an outpatient clinic appointment (timed where possible to coincide with routine clinical
957 follow-up) or by visiting the patient's home.

958
959 Given that patients will be unable to complete a baseline EQ-5D-5L questionnaire, a baseline valuation will be
960 assigned to all patients informed by the current literature. Respondents to the EQ-5D-5L will be assigned valuations
961 derived from published UK population tariffs for the EQ-5D-3L [52]and using the crosswalk value set available from
962 the EuroQol website (<http://www.euroqol.org>), or using a UK population tariff for the EQ-5D-5L if published prior to
963 the analysis of the trial. These valuations will then enable QALYs gained per patient to 6 months to be calculated.

964
965 Resource use data will be collected on the two alternative initial airway management methods delivered by
966 paramedics, resources used once in hospital such as targeted temperature management, interventions in the cardiac
967 catheter laboratory (e.g. angioplasty) and intensive care unit stay. We will also collect any resources which may be
968 related to the patient's OHCA following hospital discharge such as hospital readmissions, outpatient and Accident and
969 Emergency visits and contacts with general practice. Resource use data will either be extracted from the Hospital
970 Episode Statistics (HES) data set or be collected as part of the trial CRFs up to hospital discharge. Linkage of study

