971 data to resource use data from the HES data set will be undertaken with the prior permission of the Health Research
972 Authority Confidentiality Advisory Group (CAG). This will allow us to obtain resource use data for all patients,
973 regardless of their consent status. At 3 and 6 months data will be captured using bespoke resource use questionnaires.
974 Any hospital admissions in this follow up period will also be confirmed using the HES data set. We demonstrated the
975 ability to successfully collect these economic data during our feasibility study.

976
977 A detailed preliminary study (currently pre-publication) led by one of this proposal's co-applicants ([name]) has been
978 performed on a dataset from the London Ambulance Service and Imperial College Healthcare NHS Trust, the latter of
979 which is a major de facto cardiac arrest and heart attack centre in North West London. This has allowed us to develop
980 an understanding of the likely proportions of patients surviving to the various "way-points", and to develop the CRFs
981 to comprehensively capture the resources used, and hence the costs incurred, to then perform this patient level cost
982 effectiveness analysis in accordance with NICE guidelines. Unit costs will be derived from nationally published
983 sources and Trust finances, and attached to the resource use data.

984 Missing data will be handled using multiple imputation methods[53]. We will report the cost and quality of life data
985 for each trial group and the difference between the groups, accounting for the effect of the clustering. From the average
986 costs and QALYs gained in each trial group, the incremental cost-effectiveness ratio will be derived, producing an
987 incremental cost per QALY gained of i-gel compared to intubation [54]. Given this is a cluster randomised trial,
988 statistical methods for combining costs and outcomes will need to take account of the correlation between costs and
989 outcomes at both the individual level and also at the cluster level [55, 56]. The i-gel will be considered cost-effective
990 if the incremental cost-effectiveness ratio falls below £20,000, the level below which NICE generally recommends
991 interventions to the NHS [57]. Univariate and multivariate sensitivity analyses will show what impact varying key
992 parameters in the analysis has on baseline cost-effectiveness results. Results will be expressed in terms of a cost-

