1136 have arisen ad hoc throughout England. We need to use patient identifiable data to link ambulance service
1137 data and hospital data, to verify that different records relate to the same individual and to determine survival
1138 status for each patient.

1139

1140 b) Collect data on treatment and outcomes to hospital discharge or death (whichever occurs first) on all OHCA
1141 patients. This approval is being sought in order to access identifiable information without consent for those
1142 patients where it is not possible to obtain consent. This approach will ensure maximum data ascertainment
1143 (see section 4.6.1).

1144

1145 c) Allow NHS Digital to process patient identifiers, link them to the HES data and return the linked data back to
1146 the study team, for all enrolled patients regardless of whether or not they have provided consent for follow up.
1147 This approval is being sought to allow the health economics analysis to take place (see section 6.5).

1148

1149 **9.3 Risks and anticipated benefits**

1150

1151 Participating paramedics will benefit from additional training in resuscitation, airway management and evidence based
1152 practice during the trial. No potential harms to paramedics have been identified.

1153

1154 It is generally recognised that patients enrolled in research studies tend to have better outcomes than those not enrolled.
1155 It is possible that one study group will prove to be superior to the other, but at present clinical equipoise exists, and the
1156 trial is being undertaken to address this question. Ongoing scrutiny by the TSC and DMSC, coupled with a formal
1157 interim analysis, is designed to minimise the risk to participants, and ensure that the trial is discontinued if significant
1158 differences are identified between the two study groups.

1159

1160 Both interventions have recognised complications. These include:

1161

- 1162 • Interruptions to CPR. This is possibly more common with tracheal intubation.
- 1163 • Misplacement of the device (particularly unrecognised misplacement). This is possibly more common with
1164 tracheal intubation.

- 1165 • Regurgitation of stomach contents, and aspiration into the lungs. This is possibly more common with the i-gel
1166 SAD.
1167 • Dislodgement of the device during ongoing resuscitation and/or patient transport. This is possibly more
1168 common with the i-gel SAD.

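### The £20,000 ICER criterion in section 6.5 has no condition on the sign of the QALY difference, so read literally it is correct only if i-gel gains QALYs

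*Protocol*

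**What the plan says.** Protocol section 6.5 (Economic evaluation) takes the mean costs and QALYs by arm and forms one ratio from them: from the average "costs and QALYs gained in each trial group, the incremental cost-effectiveness ratio will be derived", giving an "incremental cost per QALY gained of i-gel compared to intubation". It then fixes the decision criterion: "The i-gel will be considered cost-effective" "if the incremental cost-effectiveness ratio falls below £20,000". The threshold is justified by reference to NICE's usual practice.

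The sentence sets no condition on the sign of the cost or QALY difference, and section 6.5 contains no dominance or net-benefit rule. It does commit the evaluation to NICE guidance, promises costs and quality of life by group together with the between-group difference, and promises a cost-effectiveness acceptability curve.

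The aim in section 3 is to establish whether i-gel is superior in "adults, in terms of both clinical and cost effectiveness". The SAP (sections 1.1 and 2.2) leaves the economic evaluation out of its scope, so section 6.5 holds the only decision rule in these documents.

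**The concern.** An ICER has the same meaning on both sides of zero only if its denominator keeps its sign. When i-gel gains QALYs, a ratio below £20,000 means that each QALY is bought for less than the threshold. When i-gel loses QALYs there are two different situations, and the rule mishandles both:

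- If i-gel also costs more, the ratio is negative and automatically below £20,000, so the option that is worse on both counts passes.
- If i-gel costs less, the ratio is the saving per QALY given up. A low value then counts against i-gel and a high value for it, which is the reverse of the written rule.

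The protocol does not treat a QALY loss as impossible. Section 9.3 says "It is possible that one study group will prove to be superior to the other" without saying which, and lists complications thought possibly more common with i-gel. If the point estimate fell on that side, the pre-specified sentence would give the opposite of the correct conclusion.

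**Working it through.** The threshold is a stated constant, so there is no computed figure of the protocol's to reproduce. The check is whether the written rule agrees with the decision it is meant to express.

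**Algebra.** Let dC and dE be the cost and QALY differences, i-gel minus intubation. The written rule is dC/dE < 20,000. The net-benefit rule is NMB = 20,000 × dE − dC > 0. If dE > 0, multiplying the first by dE gives dC < 20,000 × dE, which is the second. If dE < 0, the same step reverses the inequality and the two rules always disagree.

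**Cases.** The documents give no cost or QALY differences, so these are illustrative. The verdicts depend only on signs and ratio.

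| dC | dE | ICER = dC/dE | Written rule | NMB | Cost-effective by NMB |
|---|---|---|---|---|---|
| +£100 | +0.01 | £10,000 | yes | +£100 | yes |
| +£300 | +0.01 | £30,000 | no | −£100 | no |
| −£100 | +0.01 | −£10,000 | yes | +£300 | yes |
| +£100 | −0.01 | −£10,000 | yes | −£300 | no |
| +£100 | −0.002 | −£50,000 | yes | −£140 | no |
| −£20 | −0.002 | £10,000 | yes | −£20 | no |
| −£100 | −0.01 | £10,000 | yes | −£100 | no |
| −£300 | −0.01 | £30,000 | no | +£100 | yes |

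The first three rows agree and the last five do not. Over 1,000,000 random pairs of differences, agreement was 100% where dE > 0 and 0% where dE < 0.

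**How likely is a negative QALY estimate?** Inputs from section 4.7 are 4,535 patients per group, a rate of 9% and a design difference of 2 points. The assumption is that each survivor accrues q QALYs by 6 months and everyone else none, with the 2-point difference applied to that same proportion. The value of q is not in the documents; I take 0.35, with a range of 0.25 to 0.45.

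- SD per patient = √(0.09 × 0.91) × 0.35 = 0.286 × 0.35 = 0.100.
- SE of the difference = 0.100 × √(2/4,535) = 0.0021 (range 0.0015 to 0.0027).
- Design effect in QALYs = 0.02 × 0.35 = 0.007 (range 0.005 to 0.009).
- Ratio = 0.02 / (0.286 × 0.0210) = 3.3. The value of q cancels, so this holds for any q.

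At 3.3 standard errors above zero, the chance of a negative estimate is about 0.0004. With no true difference it is about one half. This SE ignores clustering and variation in QALYs among survivors. The clustering inflation in section 4.7 is 4,535/4,400 = 1.031, which multiplies the SE by √1.031 = 1.015 and leaves the ratio at about 3.3. Variation among survivors would lower the ratio by an amount the documents do not allow one to compute.

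**The case against.** The strongest reply is that nobody would apply the sentence so literally. Section 6.5 binds the evaluation to NICE guidance and ties the threshold to NICE practice. It also requires the between-group differences, so a costlier and less effective i-gel would be plain to see. The acceptability curve, as conventionally computed, gives at £20,000 the probability of positive net benefit, and a dominated i-gel would score low there. All this stands as a limit on the practical risk. It does not replace the written criterion. A curve built on net benefit would simply contradict the sentence beside it.

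A second reply is that a cost per QALY gained presupposes a gain. That is arguable, but the protocol uses the phrase for QALYs accrued by a patient or within an arm ("These valuations will then enable QALYs gained per patient to 6 months to be calculated"), so it does not restrict the between-arm difference to positive values.

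A third is that dominance handling belongs in a later analysis plan. As an argument against calling it missing, that is fair. The point here is narrower: the rule that is stated gives wrong answers over part of its range.

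A reader might go further and infer that the QALY difference is bound to be near zero, so that the rule has an even chance of reversing the economic conclusion. The documents do not support that. The even chance belongs to the case of no true difference; under the trial's own design effect a negative estimate is very unlikely.

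**Conclusion.** The point holds as a defect in a stated rule. As written, the criterion is correct whenever i-gel gains QALYs and wrong whenever it loses them; this is algebra and rests on no assumption about costs or utilities.

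How much it matters depends on the true effect. It matters mainly if the true QALY difference is null (a negative estimate about half the time) or unfavourable. Under the 2-point design effect the exposure is negligible, subject to the simplifications shown in the working.

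Severity is minor to moderate and confined to the economic evaluation. Because cost-effectiveness is part of the stated aim, one might infer that the aim itself is compromised. It is not: the estimates, the between-group differences and the curve are unaffected, and so are the primary clinical outcome and the sample size. Only the sentence that turns the ratio into a conclusion needs repair.

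**What to change.** Replace the criterion in section 6.5 with: i-gel is considered cost-effective if incremental net monetary benefit at £20,000 per QALY (20,000 × QALY difference − cost difference) is above zero.

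An equivalent that keeps the ICER is to:

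- apply the below-£20,000 rule only where i-gel gains QALYs;
- state dominance where one option is both costlier and less effective;
- reverse the inequality where i-gel is cheaper and less effective.

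Either version is sound, and the ratio in the cheaper, less effective case need not be suppressed so long as it is read as savings per QALY lost. The acceptability curve should be computed on the same definition.

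The cost is a change of wording in one place. No new data are needed, and no verdict changes where i-gel gains QALYs.
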